6.14.3 Vital Signs

The following vital signs will be measured:

- Systolic blood pressure (mmHg)
- Diastolic blood pressure (mmHg)
- Pulse rate (bpm)
- Respiration rate (breath / min)
- Body temperature (degrees Celsius)
- Body weight (kg)
- Oxygen Saturation (%)
- Weight (kg)
- Height (cm)

Descriptive statistics for observed values and changes from baseline for vital signs, including weight, height (measured at screening only) and BMI will be presented by treatment group and visit (Table 14.3.6.1). Also frequency table by the clinical significance will be presented for each vital sign (Table 14.3.6.2).

All results of vital signs measurements will be listed (Listing 16.2.8.4).

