## Overall Design

VMALS-002-02 is a Phase 2a, double-blind, randomized, placebo-controlled, multicenter study designed to assess the safety of Engensis (containing the active pharmaceutical ingredient VM202) in Participants with ALS. Following the completion of the informed consent process, Screening activities (within 30 days prior to Day 0) will determine which Participants meet the eligibility criteria and who will be enrolled and randomly assigned in a double-blind fashion in a 2:1 ratio to either Engensis or Placebo, respectively.

During Screening, medical history, familial cancer history, demographics, vital signs, weight and height, complete physical examination, the ALSFRS-R, slow vital capacity (SVC), 12-lead electrocardiogram (ECG), laboratory assessments (coagulation profile, serum chemistry, and hematology), viral screening, a record of all concomitant medications and procedures, and urine pregnancy test for females of childbearing potential will be conducted. Adverse event (AE) assessment will start upon completion of the consent process at the start of Screening and treatment-emergent adverse event (TEAE) assessment, including injection site reactions, will start after the first injection of Engensis or Placebo (Day 0) and continue throughout the study.

Following randomization and prior to the first IM injections of Engensis or Placebo on Day 0, vital signs and weight, a complete physical examination, urine pregnancy test, SVC, concomitant medications and procedures, measurement of muscle strength by HHD and ATLIS (at clinical study sites where available), ALSFRS-R, muscle biopsy, and the quality of life assessment with the ALSAQ-40 will be completed.

All Participants will receive 0.5-mL (0.25 mg) IM injections (2 to 20 injections per muscle, depending on the anatomical location of the muscle) of Engensis or Placebo in target muscles at each of two dosing Visits during 3 Treatment Cycles: Treatment Cycle 1 on Days 0 and 14, Treatment Cycle 2 on Days 60 and 74, and Treatment Cycle 3 on Days 120 and 134. Vital sign measurements will be performed at 2 hours after completion of IM injections of Engensis or Placebo on Days 0, 14, 60, 74, 120, and 134.

Vital signs will be recorded at all Study Visits. On Day 0, a blood sample will be collected for future genetic testing. Muscle biopsies will be collected on Day 0, 84 (optional), and 144.

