4. **Vital Signs, Weight, and Height:** Vital signs will be measured at Screening, predose, and 2 hours ( $\pm 1$  hour) post-dose at Study Injection Visits during the Treatment Cycle 1 (Days 0 and 14), Treatment Cycle 2 (Days 60 and 74), and Treatment Cycle 3 (Days 120 and 134). Vital signs will also be measured at Study Visits on Days 30, 84, 144, and 180/ET (Day 180 or Early Termination). After the Participant has rested in the seated position for 5 minutes, vital signs will be collected, including temperature, sitting blood pressure, heart rate, respiratory rate, and oxygen saturation on room air. The method of temperature measurement should be according to the Site's policy and should be consistently applied. Weight will be collected at Screening and predose at Study Injection Visits (Days 0, 14, 60, 74, 120, and 134); height will only be measured at Screening.
5. **Complete Physical Examination** will be performed at Screening, predose on Days 0, 14, 60, 74, 120, and 134, and at Study Visits on Days 30, 84, 144, and 180/ET. The examination will include the following: head, eyes, ears, nose, and throat (HEENT); heart; lungs; abdomen; extremities; lymph nodes; neurological; musculoskeletal system; and skin/integumentary systems. Any abnormalities should be categorized as clinically significant (CS) or not clinically significant (NCS), and the abnormalities should be recorded as adverse events, except at Screening.
6. **12-Lead Electrocardiogram (ECG)** will be performed at Screening, Day 84, and Day 180/ET. Any clinically significant findings at Screening will be recorded as part of the medical history. Clinically significant abnormalities are to be recorded as adverse events, except at Screening. The ECG recording must be stored with the Participant's records.
7. **Coagulation Profile** will be evaluated at Screening and will include prothrombin time (PT), partial prothrombin time (PTT), and International Normalized Ratio (INR).

---

**8. Serum Chemistry and Hematology:** Laboratory assessments will be evaluated at Screening (to establish eligibility) and on Days 60, 120, and 180/ET.

**Chemistry** includes sodium, potassium, chloride, bicarbonate, calcium, inorganic phosphate, magnesium, glucose, amylase, lipase, creatine kinase, lactate dehydrogenase, and:

- a. Kidney function tests (blood urea nitrogen, creatinine)

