6.2.2 Baseline

Baseline for safety parameters as well as for exploratory parameters is defined as the last non-missing value (either scheduled, unscheduled or repeat) before the participant receives first Study Injection.

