6.2.15 Change from baseline

QMD Ref: Worldwide-TMP-ST-005-7.0 Effective: 12Aug2019	Governing QMD: Worldwide-SOP-ST-001
Confidentiality Statement	

This document is the property of Worldwide Clinical Trials Inc. and may not be duplicated, copied, altered or removed from company without prior approval from Worldwide Quality Assurance or in compliance with Worldwide Standard Operating Procedures.

Worldwide Clinical Trials Controlled Quality Management Document		
 WORLDWIDE CLINICAL TRIALS	Sponsor:	Helixmith Co., Ltd.
	Protocol Number:	VMALS-002-2
STATISTICAL ANALYSIS PLAN VERSION 3.0		

Change from baseline will be calculated as difference value on post-baseline visit – value on baseline visit. Percentage changes from baseline will be calculated as $100 * (\text{value on post-baseline visit} - \text{value on baseline visit}) / \text{value on baseline visit}$.

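### The SAP compares post-dose vital signs at five of the six injection visits with a value 2 to 19 weeks old and leaves the same-visit predose reading unused

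*SAP*

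**What the plan says.** **Collection.** The protocol synopsis (Overall Design) states: "Vital sign measurements will be performed at 2 hours after completion of IM injections of Engensis or Placebo", and names Days 0, 14, 60, 74, 120 and 134. Footnote 4 of the Schedule of Activities says "Vital signs will be measured at Screening, predose, and 2 hours", with a window of plus or minus 1 hour on the post-dose reading. Protocol 8.2.4 repeats the predose and post-dose pair for all three cycles.

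**Analysis.** SAP 6.2.2 sets one reference value for every safety parameter, "defined as the last non-missing value (either scheduled, unscheduled or repeat) before the participant receives first Study Injection". SAP 6.2.15 subtracts that value from each later one. For vital signs, SAP 6.14.3 plans "Descriptive statistics for observed values and changes from baseline for vital signs, including weight, height (measured at screening only) and BMI", by treatment group and visit, in Table 14.3.6.1. It adds a frequency table by clinical significance (Table 14.3.6.2) and a full listing (Listing 16.2.8.4).

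**What is absent.** The SAP defines no change from the predose to the post-dose reading of the same visit. It names predose time points for laboratory tests (6.14.2), physical examination (6.14.5) and ALSFRS-R (6.15.1), but section 6.14.3 names none. SAP 6.2.14 lets only scheduled post-baseline values into the tables. The 2-hour readings are scheduled, so they qualify, but the plan does not say how they are shown next to the predose ones.

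**The concern.** The primary objective is safety, and the dosing-day load is higher than before. Protocol 4.4.2 describes 256 injections over four visits in the earlier ALS study, an average of 64 per dosing day, against 128 per dosing day here, repeated over three cycles. How vital signs respond within hours of the injections, at the later visits as well as the first, is a natural safety question, and a matched pair of readings is collected at each visit.

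The planned change score answers that question on Day 0 only. At the other five injection visits it adds together the response to that day's injections, any lasting effect of earlier injections, background change in the disease, concomitant treatment and ordinary visit-to-visit variation. The protocol itself expects respiratory decline in this population: 8.5.4.2 makes pulmonary problems adverse events of special interest. A lower oxygen saturation after dosing on Day 134 than on Day 0 therefore has more than one explanation within an arm.

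If Table 14.3.6.1 shows both time points, a reader can subtract the two mean values, provided the same participants contribute to both. The SD, confidence interval, minimum and maximum of the paired change cannot be obtained from the table that way.

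**Working it through.** **1. The plan's own figure.** Protocol 4.4 describes 6 treatment days over 19 weeks. The injection days are 0, 14, 60, 74, 120 and 134, which is six, and 134 / 7 = 19.1 weeks. The figure reproduces. The sample size of 18 comes with no alpha, power or effect size, so there is no power figure to reproduce.

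**2. Age of the reference value at each post-dose reading** (nominal day / 7):

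| Injection visit | Time since Day 0 predose |
|---|---|
| Day 0 | about 2 hours plus injection time |
| Day 14 | 2.0 weeks |
| Day 60 | 8.6 weeks |
| Day 74 | 10.6 weeks |
| Day 120 | 17.1 weeks |
| Day 134 | 19.1 weeks |

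Five of the six visits have a reference 2 to 19 weeks old. If the Day 0 predose value is missing, the baseline rule falls back to an earlier value, possibly Screening, up to 30 days before.

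**3. Precision, on assumed SDs.** The documents give no SD for any vital sign. Take systolic pressure with within-visit SD sw = 5 mmHg and visit-to-visit SD sv = 4, 8 or 12 mmHg. There is no progression term, so this shows random noise only.

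- SD of change from Day 0 = sqrt(2(sv² + sw²)). This gives sqrt(82) = 9.1, sqrt(178) = 13.3 and sqrt(338) = 18.4.
- SD of same-visit change = sqrt(2) × sw = sqrt(50) = 7.1.
- Single-arm 95% half-width = t(n − 1) × SD / sqrt(n), with t = 2.201 for n = 12 and 2.571 for n = 6.
- Half-width for the difference between arms = t(16) × SD × sqrt(1/12 + 1/6) = 2.120 × 0.5 × SD.

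| 95% CI half-width, mmHg | sv = 4 | sv = 8 | sv = 12 | Same visit |
|---|---|---|---|---|
| Engensis, n = 12 | 5.8 | 8.5 | 11.7 | 4.5 |
| Placebo, n = 6 | 9.5 | 14.0 | 19.3 | 7.4 |
| Difference, 12 versus 6 | 9.6 | 14.1 | 19.5 | 7.5 |

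**4. The same check without units.** Set the SD of a single reading to 1. Assume a correlation r of 0.7 to 0.9 between same-day readings and 0.3 to 0.6 between Day 0 and a later visit. The SD of a change is sqrt(2(1 − r)): 0.89 to 1.18 against Day 0 and 0.45 to 0.77 within visit, so the former is 1.15 to 2.65 times the latter. The half-width for the 12-versus-6 difference is 0.95 to 1.25 SD against Day 0 and 0.47 to 0.82 SD within visit.

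The direction holds whenever two readings on the same day agree more closely than readings weeks apart. The size depends on the assumptions. Participants who differ in their acute response would add variance to both change scores, so 7.1 mmHg is a best case and the true ratio would be smaller.

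**The case against.** The strongest reply is the placebo arm. The objective is a comparison with placebo, and placebo participants receive the same number of injections on the same days. Background ALS change is therefore the same in both arms in expectation. A reader might infer that disease progression biases the vital-sign comparison between arms, but a randomised concurrent control with an identical schedule does not support that. The same-visit change also needs the placebo contrast before anything can be assigned to Engensis. This stands, and it limits the point to precision and to how a within-arm change may be read.

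The second reply is that nothing is lost from the record. Listing 16.2.8.4 carries every reading, at most 18 × 6 = 108 pairs per parameter, so each acute change and outlier can be recovered. Table 14.3.6.2 does not depend on the change-score baseline. Protocol 10.2.1 counts clinically significant vital-sign abnormalities as adverse events, so they reach the TEAE tables. SAP section 6 permits added tables. All of this is correct. What remains is that a summary derived after the data are seen is weaker than a prespecified one.

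Third, a reader might infer that the protocol intended a paired analysis. It does not say so: the passages schedule the readings and give no purpose. Vital signs are neither a primary nor an exploratory endpoint, and Protocol 9.3.1 plans no formal safety testing. Finally, a single pre-treatment baseline is a coherent choice for cumulative change over three cycles, and there is no contradiction or wrong formula here.

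**Conclusion.** The point holds as a gap in the descriptive safety analysis. Only the Day 0 change is acute. At the other five injection visits the reference is 2 to 19 weeks old, the same-visit predose value is unused, and separate display of the two time points is not specified. The cost is a less precise view of the acute change in a 12-versus-6 comparison, and a within-arm change that cannot be attributed to that day's injections. On the assumed systolic SDs, the half-width for the difference between arms is 9.6 to 19.5 mmHg instead of 7.5. These figures illustrate noise only. They do not measure ALS progression, and the documents give no data on vital-sign drift.

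Severity is low to moderate, because the listing, the clinical-significance table and the TEAE tables preserve the important signals.

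**What to change.** In SAP 6.14.3 and Table 14.3.6.1:

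- Label the predose and post-dose time points at each injection visit.
- For each of the six injection visits, derive post-dose minus same-visit predose for systolic and diastolic blood pressure, pulse, respiration, temperature and oxygen saturation. Weight is collected predose only and needs no such change.
- Summarise it by arm and visit with the 95% CI for the mean, minimum and maximum, as SAP 6.3 already does for continuous variables.
- Keep all existing change-from-baseline summaries, including those for post-dose readings. They describe cumulative change, which the new variable does not.

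The cost is a few lines of SAP text, one derived variable and extra rows in an existing table. The data are already scheduled, so there is no new procedure and no added burden for participants.

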6.14.4 Electrocardiogram Data

QMD Ref: Worldwide-TMP-ST-005-7.0 Effective: 12Aug2019	Governing QMD: Worldwide-SOP-ST-001
Confidentiality Statement	

This document is the property of Worldwide Clinical Trials Inc. and may not be duplicated, copied, altered or removed from company without prior approval from Worldwide Quality Assurance or in compliance with Worldwide Standard Operating Procedures.

Worldwide Clinical Trials Controlled Quality Management Document		
 WORLDWIDE CLINICAL TRIALS	Sponsor:	Helixmith Co., Ltd.
	Protocol Number:	VMALS-002-2
STATISTICAL ANALYSIS PLAN VERSION 3.0		

Electrocardiogram will be performed at Screening, Day 84 and End of Study. Descriptive statistics for electrocardiogram results: general interpretation, abnormal findings and clinical significance will be presented by treatment groups (Tables 14.3.7.1 and 14.3.7.2).

All electrocardiogram results will be listed (Listing 16.2.8.5).

6.14.5 Physical Examination

Complete physical examination will be performed at Screening, Day 0 pre-dose, Day 14 pre-dose, Day 30, Day 60 pre-dose, Day 74 pre-dose, Day 84, Day 120 pre-dose, Day 134 pre-dose, Day 144 and End of Study.

The following body systems will be examined:

- HEENT (Head, Eye, Ear, Nose, Throat)
- Heart
- Lungs
- Abdomen
- Extremities
- Lymph Nodes
- Neurological
- Musculoskeletal System
- Skin/Integumentary Systems

Each parameter will be presented with frequencies and percentages of values (Normal, Abnormal not Clinically Significant (NCS), Abnormal Clinically Significant (CS)) in shift tables based on baseline for each treatment group (Table 14.3.6.3). Percentages will be based on the number of participants who have measurement at baseline and at corresponding post-baseline visit.

A listing of physical examination results will be presented (Listing 16.2.8.6).

6.15 Exploratory Analyses

Exploratory analyses will be performed in the ITT population.

6.15.1 Revised Amyotrophic Lateral Sclerosis Functional Rating Scale (ALSFRS-R)

ALSFRS-R will be measured at Screening, Day 0 pre-dose, Day 30, Day 60 pre-dose, Day 84, Day 120 pre-dose, Day 144 and Day 180.

QMD Ref: Worldwide-TMP-ST-005-7.0 Effective: 12Aug2019	Governing QMD: Worldwide-SOP-ST-001
Confidentiality Statement	

This document is the property of Worldwide Clinical Trials Inc. and may not be duplicated, copied, altered or removed from company without prior approval from Worldwide Quality Assurance or in compliance with Worldwide Standard Operating Procedures.

Worldwide Clinical Trials Controlled Quality Management Document		
 WORLDWIDE CLINICAL TRIALS	Sponsor:	Helixmith Co., Ltd.
	Protocol Number:	VMALS-002-2
STATISTICAL ANALYSIS PLAN VERSION 3.0		

Total score and subscores for Fine and Gross Motor Functions and for Bulbar Function and their changes from baseline will be presented with descriptive statistics by visits and treatment group (Table 14.6.1, Listing 16.2.9.1).

Slope of the total score will be provided using graphical presentation of values by visit for both treatment group.

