### **5.3. Number of Participants**

The target sample size is 18 Participants who will be randomized in a 2:1 ratio to Engensis or Placebo (12:6).

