3.2 Exploratory Endpoints

- Change from Baseline (Day 0) in total mean Revised Amyotrophic Lateral Sclerosis Function Rating (ALSFRS-R) scores at Day 180 for Engensis compared to Placebo
- Change from Baseline (Day 0) in ALSFRS-R subscores for Fine and Gross Motor Functions (sum of scores for items 4 to 9) and for Bulbar Function (sum of scores for items 1 to 3) on Days 30, 60, 84, 120, 144, and 180 for Engensis compared to Placebo
- Changes in the slope of the total ALSFRS-R score over time for Engensis compared to Placebo
- Change from Baseline (Day 0) in muscle strength assessed bilaterally by Handheld Dynamometry (HHD) in muscles in the upper and lower extremities on Days 30, 60, 84, 120, 144, and 180 for Engensis compared to Placebo
- Change from Baseline (Day 0) in the Accurate Test of Limb Isometric Strength (ATLIS) where available at Days 30, 60, 84, 120, 144, and 180 for Engensis compared to Placebo
- Change from Baseline (Day 0) in Quality of Life (QoL) using the ALS Assessment Questionnaire (ALSAQ; with 40 items, ALSAQ-40) on Days 84 and 180 for Engensis compared to Placebo
- Patient Global Impression of Change (PGIC) and Clinical Global Impression of Change (CGIC) at Days 84 and 180 for Engensis compared to Placebo
- Change from Baseline (Day 0) in Slow Vital Capacity (SVC) on Days 30, 60, 84, 120, 144, and 180 for Engensis compared to Placebo
- Time to tracheostomy for Engensis compared to Placebo
- Time to all-cause mortality by Day 180 for Engensis compared to Placebo

QMD Ref: Worldwide-TMP-ST-005-7.0 Effective: 12Aug2019	Governing QMD: Worldwide-SOP-ST-001
Confidentiality Statement	

This document is the property of Worldwide Clinical Trials Inc. and may not be duplicated, copied, altered or removed from company without prior approval from Worldwide Quality Assurance or in compliance with Worldwide Standard Operating Procedures.

Worldwide Clinical Trials Controlled Quality Management Document		
 WORLDWIDE CLINICAL TRIALS	Sponsor:	Helixmith Co., Ltd.
	Protocol Number:	VMALS-002-2
STATISTICAL ANALYSIS PLAN VERSION 3.0		

- Change from Baseline (Day 0) in biomarkers for muscle atrophy in biopsies collected before and after injections for Engensis compared to Placebo

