4 SAMPLE SIZE

A sample size of 18 Participants was chosen for safety assessments and preliminary evaluation of exploratory endpoints.

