6.1.2 ITT Population

The Intent to Treat (ITT) Population consists of all randomized participants. Participants will be grouped according to their planned treatment. Exploratory endpoints will be analyzed in the ITT Population.

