6.3 Conventions

All data listings, summaries, figures and statistical analyses will be generated using SAS version 9.4 or higher¹ unless otherwise noted.

Summaries will be presented by treatment group. Treatment group labels will be displayed as follows:

Engensis (N=XX)	Placebo (N=XX)	Overall (N=XX)
--------------------	-------------------	-------------------

Listings will be sorted in the following order: treatment group, Participant, parameter, visit or cycle unless otherwise stated. All data will be listed.

Continuous variables will be summarized by the number of non-missing observations, mean, 95% confidence interval for mean, median, standard deviation, and minimum and maximum.

Categorical variables will be summarized by presenting the frequency and percent. Percentages will be based on the number of non-missing observations or the participant population unless otherwise specified. For each variable, all categories will be shown. Zero frequencies (but not the percent) within a category will be presented.

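### The exploratory change endpoints name a comparison with Placebo, but the SAP prespecifies no baseline-adjusted treatment difference with a CI, and the Day 180 ALSFRS-R mean covers only survivors with a scheduled visit

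*SAP*

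**What the plan says.** SAP 3.2 (matching Protocol 3 and 9.3.2) words the main functional endpoint as "Change from Baseline (Day 0) in total mean Revised Amyotrophic Lateral Sclerosis Function Rating (ALSFRS-R) scores at Day 180 for Engensis compared to Placebo". The endpoints for ALSFRS-R subscores, HHD, ATLIS, ALSAQ-40 and SVC are also changes from baseline, set against Placebo.

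The analysis is in SAP 6.15.1 to 6.15.6. For ALSFRS-R, the total and the subscores for motor function and for "Bulbar Function and their changes from baseline will be presented with descriptive statistics by visits and treatment group". On slope, 6.15.1 says: "Slope of the total score will be provided using graphical presentation of values by visit for both treatment group". HHD, ATLIS and ALSAQ-40 also get descriptive statistics by visit and arm. For SVC, 6.15.6 tabulates the best, second-best and third-best volumes; it names no change from baseline.

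SAP 6.3 defines the summaries: "Continuous variables will be summarized by the number of non-missing observations, mean, 95% confidence interval for mean", followed by median, standard deviation, minimum and maximum, all by treatment group.

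On who is counted, SAP 6.1.2 says: "Exploratory endpoints will be analyzed in the ITT Population". SAP 6.2.14 puts only scheduled post-baseline values in the tables and keeps early-termination assessments for listings, although Protocol 7.2 collects ALSFRS-R at the early-termination visit. The ALSAQ-40 rule in SAP 6.2.11 covers unanswered items, not missed visits. Death is a separate Kaplan-Meier endpoint (SAP 6.15.8).

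On size, SAP 4 says: "A sample size of 18 Participants was chosen for safety assessments and preliminary evaluation of exploratory endpoints". Protocol 5.3 splits the 18 as 12 and 6.

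**The concern.** An endpoint that names a comparison is best answered by an estimate of that comparison with its uncertainty. Here the reader gets two columns of summaries, each with its own interval. Nothing prespecifies the difference or says how chance differences in baseline severity between arms of 12 and 6 are handled. SAP 6 allows further tables or tests in the study report if the data warrant them, so any contrast wanted later could be chosen after the results are seen.

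The second issue is what the Day 180 ALSFRS-R mean describes. The population is labelled ITT, but the mean includes only participants who are alive and have a scheduled Day 180 value. If a fast progressor dies or leaves early, that arm's Day 180 mean looks better. At stake is how well the preliminary evaluation of function can be read, not the safety conclusions.

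**Working it through.** **Inputs.** N = 18, 12 v 6 (Protocol 5.3). The earlier ALS study had 1 death among 18 before the 9-month visit (Protocol 2.2.6.1). The documents give no SD, baseline correlation, effect size, alpha or power. The split checks: 18 x 2/3 = 12 and 18 x 1/3 = 6. N = 18 itself was not derived from a formula, so there is no power figure to reproduce. Results below are in SD units over assumed ranges.

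**1. Endpoint against analysis**

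| Endpoint (SAP 3.2) | Analysis (SAP 6.15) | Difference with CI? |
|---|---|---|
| ALSFRS-R total and subscores, change | per-arm summaries, figures | no |
| ALSFRS-R slope | graph | no |
| HHD, ATLIS, change | per-arm summaries | no |
| ALSAQ-40, change | per-arm summaries | no |
| SVC, change | per-arm summaries of volumes; change not named | no |

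**2. Precision of a difference.** SE = SD x sqrt(1/12 + 1/6) = 0.50 SD. With t(16) = 2.120, the 95% half-width is 2.120 x 0.50 = 1.06 SD. The two per-arm half-widths are t(11)/sqrt(12) = 0.635 SD and t(5)/sqrt(6) = 1.049 SD, which sum to 1.685 SD. A reader who waits for the two printed intervals to separate is using a criterion 1.685/1.060 = 1.59 times as wide as a CI for the difference.

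Two-sided 5% power (t test) would be 16%, 33%, 47% and 80% for assumed effects of 0.5, 0.8, 1.0 and 1.5 SD. This is a reason to estimate and not to test.

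**3. Chance baseline imbalance.** The difference in mean baseline has SD 0.50 baseline SD, so it exceeds 0.5 SD with probability P(|Z| > 1) = 32%. It matters only as far as baseline predicts change.

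**4. Effect of adjustment.** Simulated mean CI width at 12 v 6 with normal data, comparing the model change = treatment + baseline with the unadjusted difference:

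| Assumed baseline-change correlation | Change in CI width |
|---|---|
| 0 | +4% |
| -0.3 | -1% |
| -0.5 | -10% |
| -0.7 | -26% |

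The simple factor sqrt(1 - rho^2), with one degree of freedom fewer, gives half-widths of 1.02, 0.92 and 0.76 SD at correlations of size 0.3, 0.5 and 0.7. It is slightly optimistic because it ignores the cost of chance imbalance in baseline.

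**5. Chance of a death by Day 180.** P(at least one) = 1 - (1 - p)^n.

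| Assumed 180-day risk p | Any of 18 | Any of 6 Placebo | Any of 12 Engensis |
|---|---|---|---|
| 2% | 30% | 11% | 22% |
| 5% | 60% | 26% | 46% |
| 10% | 85% | 47% | 72% |

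Scaling 1/18 with a constant hazard, and taking 9 months as 270 days, gives p = 1 - (17/18)^(180/270) = 3.7% and a 50% chance of at least one death. One event supports little: the exact 95% interval for 1/18 is 0.14% to 27.3%, and the same scaling then gives about 2% to 98%.

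**6. Size of the shift.** Assume normal changes and that the missing participant is the fastest progressor. The expected lowest value is -1.266 SD among 6 and -1.629 SD among 12. Without it, the arm mean improves by 1.266/5 = 0.25 SD or 1.629/11 = 0.15 SD.

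**The case against.** The strongest reply is that this is an 18-person safety study, and describing exploratory endpoints by arm is a legitimate choice. The primary safety endpoints use the same comparative wording, and Protocol 9.3.1 plans no formal testing for them. The protocol prescribes no method for the exploratory endpoints, and SAP 6.11 marks efficacy analyses as not applicable. A reader might infer that the SAP contradicts its own endpoints or the protocol; the documents do not support that. What remains is narrower: the no-testing statement covers the safety analyses only, so nothing stands in the way of an estimate with a CI.

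The unadjusted difference and its CI can also be computed from the tabulated n, mean and SD. That is true, and no document proposes judging the arms by whether their intervals overlap, so the 1.59 ratio describes a reading habit and not a planned test. The adjusted difference cannot be recovered from those tables. Nor does the plan ignore baseline, since the outcome is change from it; what is absent is adjustment for baseline.

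On death, a reader might infer that anyone who dies disappears from the results. They do not: their scheduled values before death stay in the tables, the number of non-missing observations is shown, and deaths have their own table, figure and listing. The gap is at visits after death, above all Day 180. It is also wider than death, because early-termination scores are collected and then kept out of the tables.

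Finally, a difference for every HHD muscle, ATLIS group and ALSAQ-40 item at every visit would be far too many intervals for 18 people. That stands, and it limits the fix.

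**Conclusion.** The point holds as a cheap improvement to an exploratory analysis. The SAP prespecifies no baseline-adjusted Engensis minus Placebo difference with a CI for endpoints worded as that comparison, and it does not tabulate the SVC change that its endpoint names. The Day 180 ALSFRS-R mean covers only survivors with a scheduled visit. The primary safety objective is untouched, and no stated figure is wrong.

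The size is modest and depends on assumptions. The gain from adjustment runs from a 4% wider interval to one 26% narrower, depending on a correlation that the documents do not give. Losing one fastest progressor would shift an arm mean by 0.15 to 0.25 SD, against a half-width of 1.06 SD for the difference. The chance of at least one death is about 30% to 85% for assumed risks of 2% to 10%; the single figure of about 50% should not be relied on.

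A reader might also infer that further development rests on these endpoints. The documents say only that they receive a preliminary evaluation.

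**What to change.** In SAP 6.15.1, 6.15.4 and 6.15.6, prespecify a short list: ALSFRS-R total and its two subscores, the five ALSAQ-40 subscales, and SVC. At the visits named in each endpoint, fit change = treatment + baseline value and report the adjusted Engensis minus Placebo difference with a 95% CI and no p-value. Label it exploratory, without multiplicity adjustment. That is 1 (total, Day 180) + 12 (two subscores, six visits) + 10 (five subscales, two visits) + 6 (SVC, six visits) = 29 estimates, or 39 if both ALSAQ-40 imputation tables carry them. Tabulate change from baseline in SVC and state which SVC measure is used. Leave individual HHD muscles, ATLIS groups and ALSAQ-40 items descriptive.

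The adjusted model on observed values is still conditional on survival. So for Day 180 ALSFRS-R add a supportive joint rank: deaths lowest, ordered by time of death, then survivors by change in score. Rank living participants who lack a Day 180 score on their last available score, including early termination; SAP 6.2.14 needs an exception for this. Report the rank difference between arms with a CI, by a method named in advance. Using the last score may flatter someone who left early, so state this as a limitation.

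The cost is a SAP paragraph and a few table columns, with no new data collection. The downside is an interval about 4% wider where baseline does not predict change.
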